### **Setting**

Participant recruitment will occur at Wake Forest Baptist Medical Center (WFBMC) Outpatient Nephrology Clinics, WFBMC Inpatient Nephrology Service, and the Wake Forest Outpatient Dialysis (WFOPD) units.

### **Subjects selection criteria**

The study population will consist of adult patients with incident ESKD who undergo elective initiation of HD.

### **Inclusion Criteria**

1. Age  $\geq 18$  years
2. Have CKD (including a failing renal transplant) that advanced to ESKD
3. Have elected HD for renal replacement therapy (RRT)
4. Are deemed to require dialysis initiation by the treating nephrologist or have received  $\leq 6$  sessions of intermittent hemodialysis within 30 days prior to screening
5. Have a urine output of  $\geq 500$ ml per 24 hours at the time of screening

### **Exclusion Criteria**

1. Age <18 years
2. Have urine output <500ml per day
3. Have ESKD solely as a result of severe acute kidney injury (AKI) (stage 3 AKI defined by Acute Kidney Injury Network [AKIN]) criteria)
4. Abrupt decline in kidney function preceding HD therapy initiation (i.e., if eGFR was  $\geq 30$  ml/min/1.73 m^2 within 3 months prior to the initiation of dialysis therapy)
5. Have severe systolic cardiac dysfunction with left ventricular ejection fraction <30%
6. Have an active diagnosis of hepatorenal syndrome
7. Have a significant malignancy that is likely to impact survival
8. Have a medical condition that would jeopardize the safety of the subject.

### **Sample Size**

The primary purpose of this pilot study is to evaluate the feasibility of a randomized intervention between a stepped regimen of HD and a standard regimen of HD. Therefore, for the primary feasibility outcome, we elect a pilot trial sample size of 50 patients total (25 patients per treatment group) which is consistent with recommendations for pilot and feasibility studies where samples of 10 to 20 participants per group have been deemed adequate to assess feasibility outcomes (Stat Methods Med Res 2016, 25(3), pp. 1057-1073). Power calculations for a future multicenter clinical trial will be carried out using the effect size on RKF and variability collected during this pilot study.

### **Interventions and Interactions**

Screening for potential participants will be performed at the outpatient nephrology clinics, outpatient dialysis units, inpatient nephrology service, and inpatient dialysis unit of Wake Forest Baptist Medical Center. The decision to initiate RRT is not part of the study; initiation of RRT will be deemed by patient's nephrologist. After patient's nephrologist decided that initiation of RRT is medically necessary, the overall eligibility for enrollment in this study will be reached as a consensus between the PI and the patient's nephrologist, based on the aforementioned inclusion and exclusion criteria. After written informed consent is obtained, participants will be allocated with equal probability to either incremental HD (intervention) or conventional HD (comparator) strategy. Allocation to incremental or conventional HD will be done using randomly permuted

blocks of varying sizes, stratified by the type of vascular access used at HD initiation, to maintain balance between the groups.

Hemodialysis program. Patients assigned to the intervention arm will receive a gradual HD regimen with twice-weekly HD schedule for six weeks and adjuvant medical treatment during the first six weeks of dialysis treatment, followed by thrice-weekly HD regimen onward. Patients assigned to the comparator arm will receive thrice-weekly HD at the start of dialysis therapy and onward. All participants will receive dialysis against a dialysate (bath) potassium concentration of 3.0mEq/L for their first outpatient HD treatment following randomization. All participants will use a F200 dialyzer following randomization. Beside dialysis frequency, dialyzer type and initial dialysate potassium bath, all other HD prescription parameters (e.g., treatment time, blood flow rate, dialysate flow rate) will be set and adjusted by the treating nephrologist to achieve  $\text{spKt/Vurea}$  of  $\geq 1.5$  with twice-weekly HD schedule and  $\text{spKt/Vurea}$  of  $\geq 1.2$  with thrice-weekly HD schedule. Changes in dialysate (bath) potassium concentration following the first outpatient HD treatment and/or changes in HD frequency can be done at any time during the study, as felt clinically necessary by patient's treating nephrologist. All patients will receive dietary advice and pharmacologic therapy for volume overload, hyperphosphatemia, secondary hyperparathyroidism, anemia and hypertension as guided by patient's nephrologist. According to usual care, phosphate binding agents, active vitamin D analogs, calcium-sensing receptor agonists, erythropoietin stimulating agents and intravenous iron will be used for management of hyperphosphatemia, secondary hyperparathyroidism, anemia and iron deficiency, respectively.

Adjuvant Pharmacologic Treatments/Dialysis-Sparing Therapy. Adjuvant therapy with loop diuretic, potassium-binding agent, and/or bicarbonate-based agent is expected to be necessary during the twice-weekly HD period in the intervention group. All pharmacologic treatments prescribed and administered during the study will be guided and dose-adjusted by patient's treating nephrologist. The treatment schedules described below will be used as guidance.

Treatment of hyperkalemia is summarized in Appendix B.

*Diuretic therapy.* The use of diuretic agents increases sodium and water excretion and improves volume status in dialysis patients with RKF, and has been associated with maintenance of RKF. In an observational study from the Dialysis Outcomes and Practice Pattern Study, loop diuretic use was associated with lower interdialytic weight gain, lower odds of hyperkalemia, twice the odds of retaining RKF, and a 14% lower cardiac-specific mortality (Bragg-Gresham, Am J

Kidney Dis.2007). Start dose, Furosemide, 60-80mg orally/day if uncontrolled hypertension, no discernible peripheral edema, blood pressure stable, no symptoms of congestive heart failure; or Furosemide 80-120mg orally/day if peripheral edema and/or symptoms of congestive heart failure. Dose will be titrated as needed to control hypertension (goal SBP<140mmHg and/or DBP<90mmHg measured on inter-dialytic day or pre-HD) and manage signs and symptoms of volume overload to the best extent possible.

*Hyperkalemia treatment.* All patients will receive education for low potassium diet. It is expected that 25-30% of the patients in the intervention arm will require treatment for hyperkalemia. Treatment of hyperkalemia will be determined based on baseline serum potassium level available prior to HD initiation. Based on its proven efficacy and safety in clinical trials involving patients with CKD and hyperkalemia, patiromer will be prescribed as the potassium-binding agent of choice. Treatment with patiromer will be instituted for serum potassium levels of  $\geq 5.1$  mEq/L. Patiromer will be administered daily and during the study the dose will be adjusted, as needed, based on pre-HD serum potassium levels (Appendix B). The dose of patiromer will be titrated to maintain pre-HD serum potassium of 4.6 to 5.3 mEq/L. Patiromer will be withheld temporarily or stopped for pre-HD serum potassium levels of  $\leq 4.0$  mEq/L. Participants randomized to twice-weekly HD arm who were on a potassium binder prior study enrollment and HD initiation will be continued on patiromer (if on treatment with patiromer prior to enrollment) or switched to patiromer (if on a different potassium binder prior to enrollment). Participants randomized to thrice-weekly HD who were on a potassium binder prior study enrollment and HD initiation will have the potassium binder discontinued.

*Metabolic acidosis treatment.* Treatment with Sodium Bicarbonate will be tailored based on pre-HD serum bicarbonate levels. Start dose, Sodium Bicarbonate 1300-2600mg orally/day if serum bicarbonate  $\leq 18$  mEq/L, or 650-1300mg orally/day if serum bicarbonate  $> 18$  mEq/L. Dose will be adjusted as needed for goal pre-HD serum bicarbonate levels between 20-22 mEq/L.

Participant Feedback. We developed a 24-item Patient Feedback Questionnaire to assess the following domains 5 domains: information and communication, coordination of care, perception on study-related assessments, motivation, and future studies. The answers will be rated on a 5-level scale (**Appendix F**).

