### ***Primary safety outcomes***

Time point: end of month 3

The intervention of stepwise HD schedule will be considered safe, relative to standard HD schedule, if there will be no significant difference in severe adverse events between the two HD treatment groups during the first 3 months of the study.

Severe adverse event(s) will be defined as the requirement of one or more additional HD treatment(s) or hospitalization(s) for: (1) a condition related to poor volume control (i.e., clinically-determined volume overload, decompensated heart failure, or hypertensive urgency/emergency); (2) severe electrolyte imbalance (i.e., serum potassium  $>6.5\text{mEq/L}$ ); (3) severe metabolic acidosis (i.e., serum bicarbonate  $<15\text{mEq/L}$ ); (4) symptomatic uremia (i.e., uremic encephalopathy, uremic pericarditis); or (5) death associated with study intervention.

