For evaluation of primary safety end points and secondary clinical end points, intention-to-treat principles will be followed. Evaluation of categorical end points will be performed using chi-squared tests. Evaluation of continuous end points will be performed using Student's unpaired t-test for normally distributed variables, or the Wilcoxon rank-sum test for nonparametric data. For comparison of variables measured during the time course of the study, a repeated measures analysis of variance (ANOVA) will be used. The consistency of effects on the primary end point will be explored in a variety of subgroups. Kaplan–Meier methods will be used for time-to-first hospitalization analyses. Missing RKF data for subjects will be replaced (rather than excluding them from the analysis, as missing RKF measurements might not be completely at random) using linear regression to estimate values based on other measurements for each subject (linear trend at point, SPSS). For each group-sequential analysis, the upper bound of the one-sided confidence interval for the hazard ratio (incremental HD to conventional HD) would be calculated with the use of the critical value from the Lan–DeMets–O'Brien–Fleming alpha-spending function, which preserves an overall one-sided alpha of 0.025. No adjustments for multiplicity will be made. An independent Safety Monitoring Committee will review all available data on a quarterly basis. Analyses that signal safety concerns (i.e., higher rates of hospitalization, treatment failure or death in the intervention arm compared to the comparator arm) will be reported to an independent Steering Committee to determine whether the study should be discontinued, be modified and then proceed, or continue with caution.

Descriptive statistics will be used to report the results of Participant Feedback Questionnaire.

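### Allocation is stratified by vascular access, but no named between-arm analysis is said to include access or the baseline value; if access is prognostic, continuous outcomes lose precision

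*Combined protocol and SAP*

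**What the plan says.** Under Interventions and Interactions, "participants will be allocated with equal probability to either incremental HD (intervention) or conventional HD (comparator) strategy", by permuted blocks whose size varies, "stratified by the type of vascular access used at HD initiation", with balance as the stated aim. The number of access categories and the block sizes are not given. Sample Size sets 25 patients per arm and says that the RKF effect size and variability from this pilot will be used to power a multicenter trial.

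The Analytical Plan then lists the methods:

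- Categorical end points: "Evaluation of categorical end points will be performed using chi-squared tests".
- Continuous end points: "unpaired t-test for normally distributed variables, or the Wilcoxon rank-sum test for nonparametric data".
- Measurements over time: "a repeated measures analysis of variance (ANOVA) will be used", with no list of model factors.
- Time to first hospitalisation: Kaplan–Meier methods.
- Group-sequential monitoring: a hazard ratio with a one-sided confidence bound, with no model named.

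Access type is not mentioned for any of these, nor is a baseline covariate. Subgroups are to be explored, but access is not named among them. Both pieces of data will be available: Data collection records the vascular access used, and it schedules a baseline urine collection and baseline symptom, depression and anxiety scores.

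**The concern.** Blocking within access type makes the arms more alike on access than simple randomisation would. If access also predicts the outcome, the true sampling variance of the arm difference is smaller than an unstratified formula assumes. The reported standard error is then too large and the test is conservative. For a continuous outcome, leaving out the baseline value loses precision in the same way, to the extent that baseline predicts follow-up.

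Two things are at stake. The design has already paid for balance on access, and the analysis may not collect the benefit. And the RKF standard deviation is a deliverable of this pilot: if it still contains between-access variation, the next trial will be sized on a number larger than an access-adjusted analysis needs.

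**Working it through.** **Inputs from the documents.** 50 patients, 25 per arm, 1:1, permuted blocks within access type. The sample size was chosen by pilot convention; no alpha, power, effect size or event rate lies behind it, so there is no power figure to reproduce.

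**Assumed, because the documents are silent.** Two-sided alpha 0.05; the share of variance explained by access (R²); two access strata; blocks of 4; the event rates and odds ratio below.

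**Continuous outcomes.** Ratio of unadjusted to adjusted standard error = 1/√(1 − R²). True size of a nominal 5% test = 2 × (1 − Φ(1.96 × ratio)). Sample-size inflation = ratio², because the required n is proportional to SD².

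- R² = 5%: ratio 1/√0.95 = 1.026; size 4.4%; n inflation 1/0.95 = 1.053.
- R² = 10%: ratio 1/√0.90 = 1.054; size 3.9%; n inflation 1/0.90 = 1.111.
- R² = 0: ratio 1; no inflation.

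Power for a standardised difference of 0.5 at 25 per arm (noncentral t) is 41.0% unadjusted. With adjustment it is 42.7% at R² = 5% and 44.7% at R² = 10%.

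**Binary severe-event composite.** Here R² follows from the event rates. With share f in the higher-risk stratum, R² = f(1 − f)(p₁ − p₀)² / [p̄(1 − p̄)]. At f = 50%:

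- 10% vs 20%: 0.0025/0.1275 = 2.0%, so the standard error is 1.0% too wide.
- 10% vs 30%: 0.0100/0.1600 = 6.3%, so 3.3%.
- 5% vs 35%: 0.0225/0.1600 = 14.1%, so 7.9%.

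A simulation (200,000 trials per scenario, N = 50) compared the uncorrected chi-squared test with the Cochran–Mantel–Haenszel (CMH) test stratified by access. Power is for a treatment odds ratio of 4.

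| Share at higher risk | Control rates by access | Size: chi-squared / CMH | Power: chi-squared / CMH |
|---|---|---|---|
| 50% | 10 / 10% | 4.7 / 4.6% | 47.3 / 44.8% |
| 50% | 10 / 20% | 5.1 / 5.0% | 54.8 / 53.8% |
| 50% | 10 / 30% | 4.7 / 4.9% | 55.7 / 56.9% |
| 50% | 5 / 35% | 3.9 / 4.8% | 42.9 / 49.8% |
| 70% | 10 / 10% | 4.7 / 4.5% | 47.4 / 45.0% |
| 70% | 10 / 20% | 5.2 / 4.9% | 58.4 / 57.3% |
| 70% | 10 / 30% | 5.0 / 4.9% | 61.7 / 61.3% |
| 70% | 5 / 35% | 4.5 / 5.0% | 54.1 / 57.1% |
| 80% | 10 / 10% | 4.8 / 4.6% | 47.2 / 44.8% |
| 80% | 10 / 20% | 5.4 / 5.0% | 60.4 / 59.1% |
| 80% | 10 / 30% | 5.2 / 5.0% | 64.9 / 63.2% |
| 80% | 5 / 35% | 4.8 / 5.0% | 60.3 / 60.6% |

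Stratifying raises power in 4 of 12 scenarios and lowers it slightly in 8. CMH holds its size more steadily (4.5–5.0% against 3.9–5.4%).

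**Comparison with the sample size.** At 25 per arm the planned chi-squared test has 16% power for 10% vs 20% and 42% for 10% vs 30%; 80% power would need 199 and 62 per arm. Shifts of a few points from stratifying are small beside that.

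**Time to event.** The linear-model formula does not carry over to a hazard ratio, so no inflation figure is offered for hospitalisation.

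**The case against.** A reader might infer that every standard error in the plan is too wide and that, because safety is concluded "if there will be no significant difference in severe adverse events between the two HD treatment groups", leaving out the stratum tilts the trial toward a verdict of safe. The documents do not support that. Nothing in them shows that access predicts severe events, RKF or hospitalisation, and without that there is no inflation. The stated purpose of stratifying is balance, which is achieved however the data are analysed. For the binary composite, the stratified test would more often have made a non-significant result slightly more likely, not less. Larger R² values are hard to reach for such an outcome: with a 50/50 split, 20% needs roughly 2% vs 38% event rates between access types.

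Nor is it right that every planned analysis ignores access. The ANOVA factors and the hazard-ratio model are unspecified, not shown to be unadjusted. The primary feasibility analysis is descriptive and makes no between-arm comparison. The RKF outcome is a change, so baseline enters by subtraction, though not as a covariate.

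Finally, with 48 degrees of freedom the 95% limits for a standard deviation are √(48/69.02) = 0.83 to √(48/30.75) = 1.25 times the estimate, so a 3–5% bias is small beside sampling error.

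All of this stands, and it limits the point to precision and specification. It does not answer the omission itself: nowhere does the plan say whether the one factor it stratified on enters the analysis. A systematic inflation is also avoidable, whereas the sampling error is not.

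**Conclusion.** The design and the analysis do not match as written: allocation is stratified by access, and no named between-arm method is said to use access or a baseline covariate. For continuous outcomes the cost is conditional and modest: standard errors about 3% or 5% too wide, and a future RKF sample size about 5% or 11% larger than an access-adjusted analysis would need, if access explains 5% or 10% of the variance. Those R² values are assumptions; at zero the cost is zero.

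For the severe-event composite the effect at 25 per arm is small, and its direction depends on unknown event rates. No claim should be made that the omission favours a finding of safety. The ease of reaching that finding comes mainly from N = 50 and a rule with no margin, which is a separate and larger issue. The change is worth making because it is cheap and because the RKF variability is carried forward.

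**What to change.** In the Analytical Plan:

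- Analyse RKF and the other continuous outcomes by ANCOVA or a mixed model with arm, baseline value where collected, and access type. Report the residual standard deviation for use in sizing the next trial. The baseline urine collection may fall up to a week after HD starts, so state how its timing relates to randomisation.
- Report the severe-event composite as a Mantel–Haenszel risk difference stratified by access, with a 95% CI.
- Stratify the time-to-first-hospitalisation comparison by access, and name the model behind the hazard ratio.
- Define the access categories and pre-specify how sparse ones will be pooled, for example catheter versus non-catheter.
- If access is to be left out of any comparison, say so and why.

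The cost is SAP wording and one or two degrees of freedom; no new data are needed. The downside is a slight power loss for the binary outcome if access is not prognostic: about 2.5 points in the scenarios above (47.3% to 44.8%). Sparse strata contribute little to a stratified estimate, which is why the pooling rule should be fixed in advance.

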### **Data collection**

Sociodemographic (age, sex, race, marital status, educational level, living arrangement) and clinical (ESKD etiology and comorbidities) data will be collected from all participants at enrollment, using direct patient interview and electronic medical records. Assessments of health-related quality of life (using Dialysis Symptom Index questionnaire), depression (using PHQ-9 questionnaire) and anxiety (using GAD-7 questionnaire) will be performed at enrollment and at week 6 and week 12 (month 3).

Laboratory data to include serum sodium, potassium, bicarbonate, phosphorus, calcium, intact PTH, albumin, hemoglobin, ferritin, transferrin saturation and beta-2 microglobulin will be recorded at baseline and then at set intervals according to the schedule of assessments (Appendix C).

A 24-hour urine collection will be performed at baseline (within 1 week prior to initiation of HD or within 1 week after initiation of HD). Inter-dialytic urine collection (starting with the end of one HD session and ending with the beginning of the next successive HD session) will be performed at set intervals during the study (weeks 6, 12 [month 3], 24 [month 6] and 48 [month 12] +/- 7 days). Measurements performed on urine collections will include urine volume, beta-2 microglobulin, urea and creatinine; these measurements will be used to calculate RKF (urea and creatinine clearance) and middle-molecule (beta-2 microglobulin) clearance.

Assessments of dialysis clearance using single pool Kt/V (spKt/V) and standard Kt/V (std Kt/V) will be performed according to standard of care.

Treatment with adjuvant therapy (e.g., Patiromer, Furosemide, Sodium Bicarbonate), intravenous iron, erythropoietin stimulating agent, active vitamin D and calcimimetic will be recorded as average weekly dose during weeks 0 to 6, and average weekly dose during weeks 7 to 12 (month 3). Prescription of renin-angiotensin inhibitors, beta blockers, antiplatelet therapy and/or lipid lowering medications will be recorded.

Study-specific assessments and measurements will include the Dialysis Symptom Index performed at 12 weeks (month 3), PHQ-9, GAD-7, urine collection and urine-based assays, serum measurement of beta-2 microglobulin, and serum K measurement at week 2 and 4 (Appendix C, Schedule of Assessments). Of note, baseline Dialysis Symptom, serum K measurement at week 1 and week 6, and all other aforementioned blood tests are part of standard of care.

Dialysis prescription (HD treatment time and frequency of administration, achieved blood flow, dialysate flow, potassium and calcium dialysate baths), vascular access used for HD, target weight (TW), inter-dialytic weight gain (IDWG), and ultrafiltration rate (UFR) will be recorded throughout the study. Relative IDWG will be expressed as percentage of TW when divided by the nephrologists' determined target weight. All hospitalizations and deaths (along with the cause) will be recorded from the time of enrollment to study end.

## **Outcome measures**

### ***Primary feasibility outcome***

Time point: end of study

Feasibility outcome will be assessed as the ability to recruit participants and protocol adherence. Recruitment will be determined as the proportion of people meeting inclusion criteria who ultimately consent to randomization. Protocol adherence will be determined as the proportion of participants who abide to the HD schedule, including transition from twice-weekly to thrice-weekly HD.

This pilot study will be considered successful based on attaining the following feasibility outcomes assessed at 12 months of study follow-up: (1)  $\geq 70\%$  of eligible patients are recruited, (2)  $\geq 95\%$  of participants randomized in the intervention group will adhere to the HD regimen, (3)  $\geq 80\%$  patients adhere to study-specific timed urine collection, and (4)  $\leq 5\%$  of participants randomized in the control group will cross over to a regimen of less frequent HD.

